## A . OBJECT

Menstrual disorders are one of the most common clinical symptoms in women. Since puberty, about 70% of women have experienced menstrual disorders, including early, delayed, shortened, prolonged, and more importantly oligomenorrhea, amenorrhea, and decreased menstrual flow. At present, the main method of western medicine for the treatment of menstrual disorders is hormone replacement therapy, but the incidence of adverse reactions is high, and the clinical effect is mediocre. Traditional Chinese medicine in my country mostly adopts holistic conditioning therapy for the treatment of irregular menstruation.

Zhenqi Buxue Oral Liquid consists of sheep placenta, pearl, red ginseng, wolfberry, astragalus, angelica, coix seed, ginger and jujube. The excipients are protein sugar and sodium benzoate. Nourishes qi and blood. It is suitable for dizziness, pale complexion, fatigue, lack of energy and lazy words caused by insufficient qi and blood. This study will conduct a comprehensive and in-depth study on its treatment of mental and psychological stress and menstrual disorders with "oligomenorrhea, amenorrhea, amenorrhea and decreased menstrual flow" as the main manifestations. The molecular mechanism and clinical improvement, and the safety and adverse reactions of its use will be clarified.

## B. STUDY METHOD AND DESIGN

- 330 women with menstrual disorders were observed in a prospective multi-center randomized controlled clinical trial.
- Inclusion Criteria:
  - 1) Aged between 25 and 40 years old;
  - 2) Patients with oligomenorrhea or oligomenorrhea or menopause within three months (see Appendix 1: Diagnostic Criteria of Traditional Chinese and Western Medicine)
  - 3) Meet the clinical medication conditions for progesterone to regulate menstruation
  - 4) The research subjects were informed and voluntarily participated in this study, and signed the informed consent at the same time.
- Exclusion Criteria:
  - 1) Age <25 years or >40 years old, pregnant or breastfeeding women
  - 2) Ovarian dysfunction caused by local ovarian surgery, radiotherapy and

chemotherapy for previous malignant tumors, taking hormones or immunosuppressive drugs;

- 3) Combined with serious or unstable physical diseases that may affect the efficacy of drugs and the conduct of trials, including liver, kidney, gastrointestinal, cardiovascular, respiratory, endocrine, neurological, immune or blood system diseases, etc., mental patients .
- 4) Those who were allergic to the drugs used in the trial or had serious adverse reactions in the past;
- 5) Breast cancer or family history of breast cancer in first-degree relatives, irregular vaginal bleeding, uterine fibroids ( $\geq 3$ cm), endometriosis, atypical endometrial hyperplasia, endometrial cancer and other hormone-dependent reproduction Systemic diseases and other malignant tumors;
- 6) Those with a history of thromboembolic disease or thrombosis;
- 7) Participated in a clinical trial of another research drug within 3 months prior to inclusion in this study (the first interview);
- 8) Those who have used related drugs in the past 3 months or have abused or depended on substances (alcohol or drugs) in the past 3 months; heavy smokers (smokers who smoke 20 or more cigarettes per day);
- 9) Those who met the inclusion criteria, did not follow the doctor's advice, were unable to judge the curative effect or were unable to evaluate the curative effect due to incomplete data.

➤ Methods: The participants were divided randomly into 3 groups:

- 1) Experimental group1(Zhenqi Buxue Oral Liquid): Zhenqi Buxue Oral Liquid, 10 ml each time, 2 times a day for 3 menstrual cycles, orally
- 2) Experimental group2(Zhenqi Buxue Oral Liquid and Progesterone Capsules): Zhenqi Buxue Oral Liquid was taken orally, 10 ml at a time, twice a day for 3 menstrual cycles + orally from the second half of menstrual cycle, Progesterone Capsules 200mg, once a day for 10 days for 3 menstrual cycles
- 3) Active Comparator group (Progesterone Capsules): Progesterone Capsules 200mg, qd\*10 days\*3 menstrual cycles, orally

- Treatment Period: 3 month.
- Outcomes Measurement:
  - 1) Primary Outcome: Menstrual improvement in women including cycle period, menstrual volume, number of days with bleeding or spotting, monthly rates of amenorrhea
  - 2) Secondary Outcome:
    - a) Sex hormone levels: mainly FSH, LH, E2 and AMH
    - b) AFC: Changes in AFC in pelvic ultrasonography
    - c) SF-36: The change of the MOS item short from health survey
  - 3) Safety Assessment: Adverse reactions, Hepatic Function, Renal Function, Blood Glucose, Breast Ultrasound

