### **Enrollment (Day 1)**

- a) Re-evaluate whether the subjects can enter the study according to the test and examination results during the screening period, referring to the inclusion and exclusion criteria;
- b) Subjects were enrolled and received medicines according to the random number table;

c) The investigator and the subject agree on the time of the next follow-up visit.

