**Follow-up 2 (After taking the medicine in the second month, follow-up by WeChat or telephone)**

- a) Ask and record adverse events that have occurred since enrollment;
- b) Ask the patient about the second menstrual condition (menstrual period, cycle, menstrual volume) and the symptoms of irregular menstruation after taking the medicine and make a score;
- c) The investigator and the subject agree on the time of the next follow-up visit.

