**Follow-up 3 (the third month after taking the medicine, equivalent to the end of the third month)**

- a) Ask and record adverse events that have occurred since enrollment;
- b) perform routine physical examinations (heart rate, blood pressure, weight);
- c) Ask the patient about the current menstruation and irregular menstruation symptoms, (or pregnancy), perform symptom scores, and evaluate the effectiveness of the drug;
- d) FSH, LH, E2, PRL, T, AMH (blood draw on day 2-3 of menstruation);
- e) Liver and kidney function;
- f) Pelvic ultrasound (bilateral ovarian AFC) examination, breast ultrasound;
- g) Subject returns untaken medication and checks (including used medication packaging) and filled diary card.

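### Exclusion item 9 removes randomised women whose response cannot be judged, and Section D has no all-randomised analysis, so the arm comparison can be biased

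*Combined protocol and SAP*

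**What the plan says.** Section B, exclusion item 9, begins "Those who met the inclusion criteria, did not follow the doctor's advice" and continues with women who "were unable to judge the curative effect or were unable to evaluate the curative effect due to incomplete data". It is the only text in the document that says what happens to non-adherent or unevaluable women, and it says they are excluded.

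Section C fixes the timing. On Day 1 staff "Re-evaluate whether the subjects can enter the study according to the test and examination results during the screening period", and then "Subjects were enrolled and received medicines according to the random number table". Follow-up 3, at the end of the third month, is where staff "perform symptom scores, and evaluate the effectiveness of the drug". The same visit schedules "FSH, LH, E2, PRL, T, AMH (blood draw on day 2-3 of menstruation" and the return of unused medication and the diary card.

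Section D gives the software, mean and SD, an unpaired t-test or chi-square test, a 0.05 threshold and descriptive adverse-effect comparisons. It defines no analysis population and gives no rule for missing data or withdrawals.

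**The concern.** An eligibility rule should use only what is known before allocation. Two of item 9's three grounds use information that exists only after treatment, so they act as removal rules within a randomised comparison. Section D contains nothing to offset this.

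With no true difference between arms, such removal causes bias when it depends on outcome and also differs by arm. There are grounds to expect each:

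- **Dependence on outcome.** The trial enrols women with infrequent or absent periods. A woman with no menses at month 3 has no cycle day 2-3 on which to draw the hormone sample, and no new cycle length to report. The documents do not say whether she counts as incomplete. If she does, a treatment failure is dropped.
- **Difference by arm.** The three regimens are visibly different (oral liquid, capsules, or both) and no blinding is described. A judgement that the effect cannot be assessed could be made more readily in one arm than in another.

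The arm that loses more unimproved women then looks better than it is, and no analysis listed in Section D would show it.

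**Working it through.** **Timing of the three grounds in item 9**

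| Ground | When it can be known |
|---|---|
| Advice not followed | During screening, or later: Follow-up 3 includes "Subject returns untaken medication and checks (including used medication packaging) and filled diary card" |
| Effect cannot be judged | Only after medicine is given on Day 1 |
| Effect cannot be evaluated, data incomplete | Only after follow-up |

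**Size: illustration only.** The plan has no figure to reproduce here. It gives a total of 330 women in three groups and a 0.05 threshold, but no allocation ratio, response rate, dropout rate or sidedness. Assumed: equal allocation (330 / 3 = 110 per arm), a binary failure outcome, the same true failure rate *p* = 0.40 in both arms, and a two-sided pooled two-proportion z-test.

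Let *rf* and *ri* be the shares of failures and improvers removed from an arm. The expected failure rate among those left is

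*p*(1 − *rf*) / [*p*(1 − *rf*) + (1 − *p*)(1 − *ri*)].

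For 30% versus 5% of failures removed and no improvers removed:
- Arm A: 0.40 × 0.70 = 0.28, and 0.28 / (0.28 + 0.60) = 31.8%.
- Arm B: 0.40 × 0.95 = 0.38, and 0.38 / (0.38 + 0.60) = 38.8%.
- False gap: 7.0 points.

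Rejection rates come from simulation under no true difference, 400,000 replicates per case.

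| Removed, arm A vs arm B | Failure rate left, A vs B | Gap (points) | Rejection |
|---|---|---|---|
| Failures 10% vs 10% | 37.5% vs 37.5% | 0 | 5.0% |
| Failures 10% vs 5% | 37.5% vs 38.8% | 1.3 | 5.4% |
| Failures 20% vs 5% | 34.8% vs 38.8% | 4.0 | 9% |
| Failures 30% vs 5% | 31.8% vs 38.8% | 7.0 | 18% |
| Failures 30% vs 5%, improvers 15% vs 5% | 35.4% vs 40.0% | 4.6 | 10% |
| Everyone 30% vs 5%, regardless of outcome | 40.0% vs 40.0% | 0 | 5% |

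**Sensitivity to the assumed failure rate.** For *p* from 0.20 to 0.60, the 10% versus 5% case gives a gap of 0.8 to 1.4 points and rejection of 5% to 6%. The 30% versus 5% case gives 4.3 to 7.6 points (largest near *p* = 0.55) and 13% to 19%.

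**Effect of keeping everyone.** A separate simulation used 50% improvement in both arms and 200,000 runs. Removing 0% versus 30% of non-improvers gave a false gap of 8.8 points and 24% rejection. Analysing all randomised women, with the removed women counted by their true outcome, returned 5%.

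**The case against.** The strongest defence is that item 9 is listed as an exclusion criterion, and the plan applies those criteria only at screening and on Day 1 before allocation. No text says a randomised woman is dropped from analysis. On that reading, incomplete data would mean incomplete screening data. This does not stand for the two evaluability grounds: they concern women who already qualified, and there is no curative effect to judge before medicine is given. It stands in part for the adherence ground, which could apply during screening. The medication check at Follow-up 3 has no threshold and is not linked to item 9, so its use for removal is an inference.

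Second, the primary outcome in Section B already includes monthly amenorrhea rates, and menstruation is asked about at every follow-up. Absence of menses is therefore partly counted as an outcome, and the day 2-3 hormone sample is secondary. This is fair and narrows the point. Cycle length remains undefined without a new bleed, and no rule says whether such a woman is incomplete.

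Third, every numerical input is assumed, including a binary failure that the plan does not define. Material inflation in the illustration needs a four- to six-fold imbalance in the failures removed; the mild case stays close to nominal. This also stands. The figures show what the rule permits, not what will happen.

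**Conclusion.** The plan is wrong as written and must be fixed. Item 9 is a stated rule that, if followed, removes randomised women on post-treatment grounds, and Section D provides no all-randomised analysis to protect the comparison. This conclusion rests on the text and the visit timing, not on the simulation.

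The size of any bias cannot be known from the documents. Across the assumed cases it runs from nothing (removal equal between arms or unrelated to outcome) to about 7 points and 18% rejection at a nominal 5%. Those figures depend on 110 per arm, 40% failure in both arms, a binary endpoint and a two-sided test.

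**What to change.** 1. Delete item 9 from the exclusion criteria, or keep it only to define a secondary per-protocol set.
2. State in Section D that the primary analysis includes every randomised woman in her allocated arm.
3. Keep collecting the scheduled menstrual outcomes at Follow-ups 1 to 3 from women who do not adhere or who stop. Record a month without menses as an observed outcome, not as incomplete data.
4. Prespecify one method for outcomes still missing, such as likelihood-based repeated measures or multiple imputation. Which of these is chosen is secondary. Both assume data are missing at random, so add a sensitivity analysis that varies the assumed outcome of missing women by arm.
5. Counting missing women as not improved can serve as one extreme, once improvement is defined. It is a bound, not a correction. In the mixed case above it gives 0.40 + 0.60 × 0.15 = 49% failure against 0.40 + 0.60 × 0.05 = 43%, a gap of 6.0 points in the opposite direction.
6. Report exclusions and missing data by arm, with reasons.

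The cost is one deleted or moved criterion, added text in Section D, a definition of improvement, and some extra follow-up and analysis effort. Follow-up 2 is already a "follow-up by WeChat or telephone" contact, so no visits or patients are added. The estimate may become less favourable. Section B is partly in the past tense; if follow-up is already complete, item 3 may be limited to retrieving data already recorded, while the analysis text can still be changed.

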## **C. TECHNICAL ROUTE**

### **Screening Period (Day -30~0)**

- a) The researcher explained the research situation and informed the subjects, and the subjects signed the informed consent;
- b) Evaluate whether subjects can enter the study according to the inclusion and exclusion criteria;
- c) Collect basic information, medical history (including menstrual history, pregnancy and birth history) and demographic data, conduct routine physical examination (heart rate, blood pressure, height, weight); and irregular menstrual symptoms and scoring
- d) On the 2nd to 3rd day of the menstrual cycle (basic day), draw venous blood to check FSH, LH, E2, prolactin (PRL), testosterone (T), and AMH;
- e) Liver and kidney function;
- f) Pelvic ultrasound: on the 1st to 3rd day after menstruation is clean, after disinfection of the vulva, transvaginal ultrasound is performed to count bilateral ovarian AFC, breast ultrasound;
- g) The investigator and the subject agree on the time of the next follow-up visit.

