**Follow-up 1 ( equivalent to the end of the first month)**

- a) Ask and record adverse events that have occurred since enrollment;
- b) Ask the patient about the first menstrual condition (menstrual period, cycle, menstrual volume) and symptoms of irregular menstruation after taking the medicine and make a score;
- c) The investigator and the subject agree on the time of the next follow-up visit.

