**D. STATISTICS ANALYSIS**

Data was analyzed using SPSS Version 25. All quantitative information are expressed as mean values  $\pm$  standard deviation (SD). Statistical significance was assessed using unpaired Student's t-test or chi-square test. Probability values of less than 0.05 were considered significant and an asterisk identifies such significance in the figures. We will also compare the adverse effect of each group using descriptive statistics.

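### Cycle period is a primary component with no rule for women who complete no cycle by month 3; a t-test on completed cycles omits them because of their outcome and can shrink or distort the group difference

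*Combined protocol and SAP*

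**What the plan says.** Section B (Outcomes Measurement) defines the primary outcome as "Menstrual improvement in women including cycle period, menstrual volume, number of days with bleeding or spotting, monthly rates of amenorrhea". It does not rank the components, fix a time point or say what counts as improvement in cycle period.

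Section D states that "Statistical significance was assessed using unpaired Student's t-test or chi-square test" and that quantitative data are summarised as mean ± SD. It assigns no test to any outcome and names no analysis set, missing-data rule or method for censored data.

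Inclusion criterion 2 admits "Patients with oligomenorrhea or oligomenorrhea or menopause within three months", and section A describes the target condition as "oligomenorrhea, amenorrhea, amenorrhea and decreased menstrual flow". Section C places the last visit, Follow-up 3, at the end of the third month, with nothing later.

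On data collection, the screening visit says "On the 2nd to 3rd day of the menstrual cycle (basic day), draw venous blood to check FSH" and other hormones. Follow-up 1 says "Ask the patient about the first menstrual condition (menstrual period, cycle, menstrual volume" and so on, and Follow-up 2 says "Ask the patient about the second menstrual condition (menstrual period, cycle, menstrual volume". Follow-up 3 asks about current menstruation and collects a diary card. Bleed dates are not specified anywhere.

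The only text on incomplete data is exclusion criterion 9. It lists, among others, those who "were unable to judge the curative effect or were unable to evaluate the curative effect due to incomplete data".

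**The concern.** A cycle has a length only once the next bleed has come. In women with long or absent cycles, some will have completed none when observation stops at about 90 days. The plan gives them no value, so a comparison of mean cycle length leaves them out, and exclusion 9 points the same way. That is selection after randomisation on the outcome itself. The women lost have the longest cycles, and more of them are lost from the group with longer or more variable cycles.

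The contrast most exposed is the oral liquid alone (group 1) against progesterone (group 3). If progesterone gives regular cycles and the liquid does not, group 1 loses its longest cycles while group 3 loses almost none, and the liquid looks closer to the active comparator than it is.

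**Working it through.** The plan has no figure to reproduce here: 330 women is given without effect size, SD or power, and there are no cycle lengths. What follows is a simulation on stated assumptions.

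**From the documents:** an observation window of about 3 months, taken as 90 days; three groups; a screening period of Day -30 to 0.

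**Assumed:** cycle length = group median × exp(B) × exp(W), with B normal between women (SD shown as log-SD) and W normal within women (SD 0.15). Where counts are given, 110 women per group (330/3; the allocation ratio is not stated).

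**Two ways a first cycle can start:**
- *Screening bleed:* a bleed falls uniformly on Day -30 to 0, and one later bleed by day 90 completes a cycle.
- *No screening bleed:* the first bleed falls at a random point within a cycle after Day 1, and two bleeds by day 90 are needed.

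**True difference.** Mean = median × exp((log-SD² + 0.15²)/2).
- Log-SD 0.5: exp((0.25 + 0.0225)/2) = 1.146, so 60 v 45 days gives (60 − 45) × 1.146 = 17.2 days.
- Log-SD 0.15: exp((0.0225 + 0.0225)/2) = 1.023, so 35 v 30 days gives 5 × 1.023 = 5.1 days.

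**Difference seen** when each woman's mean completed cycle is used and women with none are omitted:

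| Medians (days) | Log-SD | True | Seen, screening bleed | Seen, no screening bleed |
|---|---|---|---|---|
| 35 v 30 | 0.15 | 5.1 | 5.1 | about 5.0 |
| 35 v 30 | 0.5 | about 5.7 | 4.9 | about 3.1 |
| 60 v 45 | 0.15 | about 15 | about 15 | 10.9 |
| 60 v 45 | 0.3 | about 16 | 13.3 | 7.8 |
| 60 v 45 | 0.5 | 17.2 | 9.8 | about 5.4 |
| 75 v 60 | 0.5 | about 17 | 7.0 | about 3.7 |

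At 60 v 45 days with log-SD 0.5, about 85% v 95% of women contribute when there is a screening bleed. That leaves roughly 16 of 110 (110 × 0.15) against 6 of 110 (110 × 0.05) without a value. Without a screening bleed, 51% v 71% contribute.

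**A contrast shaped like group 1 v group 3** (progesterone median 32 days, log-SD 0.10; liquid-only median 60, log-SD 0.5): true difference 36 days; seen about 24 with a screening bleed and about 11 without.

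**Direction.** With unequal spreads the bias need not be towards zero.
- Keep the progesterone group as above and set the liquid-only median to 30 days. True difference: 30 × 1.146 − 32 × exp((0.01 + 0.0225)/2) = 34.4 − 32.5 = +1.9 days. Without a screening bleed, −2.4 is seen.
- In a separate model in which every woman starts a bleed on Day 1, equal means of 50 days with SDs of 10 and 35 gave a false difference of −9.3 days, significant in about 98% of runs.

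**The case against.** **The plan never says that the t-test uses completed cycles only.** True: no test is assigned to any outcome, and a chi-square on improved or not improved would also fit section D. But improvement in cycle period is not defined, and an unfinished cycle has no length to average. Entering the elapsed time as if it were complete would also shorten the long cycles. The gap stands, though the completed-cycle t-test is the natural reading rather than a stated one.

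**A reader might infer that every woman with a cycle running at month 3 is lost.** The documents do not support that. At a calendar visit nearly every woman has a cycle running, and anyone with one completed cycle can contribute it.

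**The largest losses need women without a screening bleed, yet screening schedules a day 2-3 draw for all.** This stands. The last column of the table applies to women who have no such bleed, whose share is unknown, and is not a trial-wide figure. Requiring a bleed within 30 days would also favour women with shorter cycles. With an assumed selection probability of 30/cycle length, and treatment scaling the cycle, the 60 v 45 case (log-SD 0.5) becomes true 13.8, seen 10.1. The loss is then 1 − 10.1/13.8 = 27%, against 1 − 9.8/17.2 = 43% without that selection. At 75 v 60 days it remains material (13.3 against 7.6).

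**The amenorrhoea rate covers these women.** In part: those who stay amenorrhoeic are counted there. It gives them no cycle length, and no rule says how the two components are read together.

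**The Follow-up 3 draw on day 2-3 of menses might imply waiting for a bleed.** No rule says so, and the visit is tied to the end of the third month.

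**Conclusion.** The gap holds, within limits. Cycle period has no rule for a woman with no completed cycle by the last visit, and the methods offered would omit her because of her outcome. The defect is confined to this one of four primary components.

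Its size rests on assumed cycle lengths, spread and start of cycle. With a screening bleed it runs from negligible (35 v 30 days, little spread) to material (60 v 45 days, log-SD 0.5: true 17, seen about 10). Women enrolled only for reduced flow may have ordinary cycles and would lose little.

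A reader might infer that the bias always shrinks the difference. Shrinkage is usual when one group simply has longer cycles, but unequal spread can reverse the sign or create a difference. Nor do the documents support any single figure for the loss in this trial. Appendix 1, cited for diagnostic criteria, was not available. The point should be fixed; confidence is medium.

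**What to change.** 1. State that exclusion 9 is not applied after randomisation to remove a woman for lack of a completed cycle.
2. Record bleed dates on the existing diary card or at the follow-ups, and define a bleed.
3. Report completed cycle length with the number of women contributing in each group, and say in advance that it is read with the monthly amenorrhoea rate.
4. Do not rest the cycle-period conclusion on the completed-cycle t-test alone. Add a pre-specified analysis that includes every randomised woman. One option is time from Day 1 to the next bleed, censored at the last visit (Kaplan-Meier with log-rank or Cox, available in SPSS), with a rule for pregnancy. Another is a binary cycle outcome defined for every woman. The choice between them is open.

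**Cost:** SAP wording, one derived variable, possibly one date field, and one extra analysis. Time to first bleed is not cycle length. It includes a cycle begun before treatment and may partly reflect progesterone timing in groups 2 and 3. It also has less power when cycles are short: at 35 v 30 days with log-SD 0.3, 39–65% for log-rank against 86–94% for the t-test (the lower figure in each pair is without a screening bleed). At 60 v 45 days with log-SD 0.5 it has more, 69–95% against 57–90%. The reason to add it is to keep all randomised women, not to gain power.

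Separately, section B counts dosing in three menstrual cycles but gives the treatment period as three months. In women with long cycles these differ, and the two statements must be reconciled.

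### The primary tests ignore presenting disorder and baseline menstrual values, although the trial mixes several disorders and can collect both before allocation

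*Combined protocol and SAP*

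**What the plan says.** All references are to the combined protocol and SAP.

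- **Target population.** Section A names the main manifestations as "oligomenorrhea, amenorrhea, amenorrhea and decreased menstrual flow". Inclusion criterion 2 in Section B admits "Patients with oligomenorrhea or oligomenorrhea or menopause within three months" and refers to Appendix 1, which is not in the text available for review. The criterion repeats one term and does not literally name scanty flow, which the objective does.
- **Primary outcome (Section B).** "Menstrual improvement in women including cycle period, menstrual volume, number of days with bleeding or spotting, monthly rates of amenorrhea". Improvement is not defined. There is no rule for combining the components, and no component is tied to a presenting disorder.
- **Size and allocation.** Section B states that "330 women with menstrual disorders were observed in a prospective multi-center randomized controlled clinical trial" and that "The participants were divided randomly into 3 groups". Under Enrollment (Day 1) in Section C, "Subjects were enrolled and received medicines according to the random number table". No allocation ratio and no stratification by disorder are stated.
- **Analysis (Section D).** "Statistical significance was assessed using unpaired Student's t-test or chi-square test". No covariate, baseline value or disorder term is mentioned.
- **Information before allocation (Section C, Screening Period).** Menstrual history and a score for irregular-menstruation symptoms are collected before the Day 1 assignment.

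**The concern.** Women who enter with different menstrual disorders start from different levels of cycle length, volume, bleeding days and months without a period. Much of that spread is predictable from the diagnosis that made them eligible. A two-sample test that ignores it treats predictable spread as noise, which widens the confidence interval for the treatment difference.

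A second effect may add to this. If a sizeable share of women are already normal on a component, treatment may have little to correct in them, and the all-women average is then smaller than the effect in the women with the problem.

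Both effects make the arms look more alike. That matters here because the comparator is active and no superiority or non-inferiority hypothesis is stated, so an imprecise null result could be misread as similarity to progesterone.

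**Working it through.** **The plan's own figure.** The total of 330 cannot be reproduced: no effect size, SD, rate, power or dropout is given. Working backwards, with 1:1:1 allocation assumed (110 per arm), two-sided alpha of 0.05 and one pairwise comparison, the difference detectable with 80% power is (1.960 + 0.842) × √(2/110) = 0.378 SD.

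**Assumed inputs, none from the documents.** f is the share of women abnormal on a component, d the effect in those women in within-disorder SD units, and k the gap in mean level between abnormal and normal women in the same units.

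**Formulas.**
- SD seen by the unadjusted test: √(1 + f(1−f)k²).
- SD after adjusting for presenting disorder: about 1.
- Average effect over all women, if those normal at entry gain nothing: f × d.
- Power: Φ(effect ÷ (SD × √(2/110)) − 1.960), with √(2/110) = 0.1348.

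**Step 1: error term alone, no dilution.** Let every woman gain 0.378 SD, with f = 1/2.
- Adjusted: 80% power.
- Unadjusted, k = 1: SD = √1.25 = 1.118; 0.378 ÷ (1.118 × 0.1348) = 2.51; power 71%.
- Unadjusted, k = 2: SD = √2 = 1.414; 0.378 ÷ (1.414 × 0.1348) = 1.98; power 51%.

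**Step 2: error term plus dilution.** Let d = 0.5, with no effect in women normal at entry.

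| f | Average effect (SD) | Adjusted | Unadjusted, k = 1 | Unadjusted, k = 2 |
|---|---|---|---|---|
| 2/3 | 0.333 | 70% | 61% | 44% |
| 1/2 | 0.250 | 46% | 38% | 26% |
| 1/3 | 0.167 | 24% | 20% | 14% |

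For f = 1/2 and k = 1: 0.25 ÷ 0.1348 = 1.854, giving Φ(−0.106) = 46%; and 0.25 ÷ (1.118 × 0.1348) = 1.658, giving Φ(−0.302) = 38%. The adjusted figure is about 45% with the noncentral t, or if the small extra variance from unequal effects is kept in the residual.

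Adjustment recovers the loss between columns. It does not undo dilution: with d = 0.5 and every woman able to respond (f = 1), power would be 96%.

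**Step 3: how far dilution depends on assumptions.** At d = 0.8 and f = 1/2, pooled power is still 84%. At f = 1 there is no dilution.

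**Step 4: would restricting the main analysis be better?** Using only women abnormal at entry gives 110f per arm and effect d. For d = 0.5 and no gap in level, power is 86%, 75% and 57% at f = 2/3, 1/2 and 1/3, against 70%, 46% and 24% using all women. That assumes exactly zero effect in the others. If they receive a fraction g of the effect, the all-women analysis wins once f + (1−f)g > √f, that is, g > (√f − f) ÷ (1 − f): 0.45, 0.41 and 0.37 at f = 2/3, 1/2 and 1/3.

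**The case against.** A reader might infer that every primary component is diluted because only women abnormal on it can improve, and that the main comparison should therefore be confined to them. The documents do not support this.

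- **Pooling on each component is inferred from silence.** Section D names tests but neither components nor an analysis population. The primary outcome could be read as one overall judgement on each woman's own complaint, and Follow-up 3 does ask for symptom scores and an evaluation of effectiveness. On that reading this dilution would not arise. This stands, although no such responder outcome is defined.
- **The share abnormal may be near 1 for some components.** Infrequent and absent periods both mean an abnormal cycle, and both can produce months without a period. Only scanty flow with regular cycles would dilute those two components. Inclusion criterion 2 as worded does not clearly admit such women, so their share could be small. This stands.
- **Inability to improve is an assumption.** Volume and bleeding days are continuous and can change in any woman, though a change from normal need not be an improvement. This stands.
- **Restriction has its own costs.** It would give each component its own primary population, demote the comparison of all randomised women, and need cut-offs for abnormality that the plan lacks. By Step 4 it can also lose power. This stands.
- **Chance imbalance in disorder mix is not a bias.** The randomised test's standard error already covers it. Correct: adjustment corrects the estimate for the observed imbalance and gains precision, but it does not remove a bias.

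None of this defends leaving presenting disorder and baseline values out of the analysis. Collecting menstrual history at screening makes adjustment possible, but the plan does not use it.

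**Conclusion.** The concern holds in a limited form. The plan mixes several disorders and specifies only unadjusted two-sample tests, although presenting disorder and baseline menstrual information are available before allocation. That gives up precision without need. Dilution is possible where many women are normal at entry, most plausibly for volume and bleeding days, but it is not established for every component.

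The size cannot be fixed from the documents. Under the assumptions above, a 1 SD gap between disorders at f = 1/2 takes power from about 45% to 38% with dilution, or from 80% to 71% without it. A smaller gap costs less. The figures rest on assumed 1:1:1 allocation, a two-sided test, complete data, and assumed values of f, d and k. They apply to continuous components.

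**What to change.** 1. Record the presenting disorder or disorders as a coded field on Day 1, before the random number is used.
2. In Section D, replace the unadjusted primary tests with models on all randomised women: a linear model for continuous components and a logistic model for binary ones. Include treatment group, presenting disorder and, where collected, the baseline value of that component. State how a woman with no recent period is handled when she has no baseline volume or bleeding days.
3. For the logistic models, state the effect measure to be reported, because an adjusted odds ratio is not the same quantity as the crude comparison behind a chi-square test.
4. Report the result in women abnormal on each component at entry as a pre-specified supportive analysis, with the cut-offs written down in advance and the share of women abnormal on each component tabulated by arm. Keep the all-randomised comparison as the main one.
5. Reconcile the wording of inclusion criterion 2 with the disorders named in Section A, so that the categories of the disorder factor are clear.

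The cost is one form field, some SAP wording and slightly more analysis work; the cut-offs in item 4 need clinical agreement. No extra women or visits are needed.
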